### **N/A**

Assigned to a form that has been marked as Not Applicable or occurs on a visit or procedure that was marked as Not Applicable.

## **10.6.3 Study Data Flow**

### **Validation**

As online forms are declared as Completed, the data monitor validates the data and either raise a query or locks the form. If the data is accurate and the monitor has no questions, the form can be validated by clicking the Validate button (shown for Completed and Amended forms) in the DM Console. After all queries have been resolved, the form can be **Locked**.

### **Queries**

Raising a query sends the form and a question back to the person who entered the data within OnCore. A queried form can be amended and then validated and locked. The process of querying and amending a form may have multiple iterations.

### **Database lock**

In OnCore, individual validated forms are locked, preventing further edits. After all forms are validated, the database is essentially locked.

## **10.7 Data Export & Reporting**

### **Data export formats**

OnCore's Biostat Console is used to extract data from OnCore for use in statistical analysis tools. The subject's full name is never included in the export. The Biostat Console can also be used to view the current progress of protocols related to accruals, forms, and adverse events. From the Data Export page, selected data can be exported into Excel spreadsheets or files formatted for easier import into SAS.

## 11 APPENDICES

### 11.1 ECOG Performance Status

Grade	Description
0	Normal activity. Fully active, able to carry on all pre-disease performance without restriction.
1	Symptoms, but ambulatory. Restricted in physically strenuous activity, but ambulatory and able to carry out work of a light or sedentary nature (e.g., light housework, office work).
2	In bed <50% of the time. Ambulatory and capable of all self-care, but unable to carry out any work activities. Up and about more than 50% of waking hours.
3	In bed >50% of the time. Capable of only limited self-care, confined to bed or chair more than 50% of waking hours.
4	100% bedridden. Completely disabled. Cannot carry on any self-care. Totally confined to bed or chair.
5	Dead.

\*As published in Am. J. Clin. Oncol.: *Oken, M.M., Creech, R.H., Tormey, D.C., Horton, J., Davis, T.E., McFadden, E.T., Carbone, P.P.: Toxicity And Response Criteria Of The Eastern Cooperative Oncology Group. Am J Clin Oncol 5:649-655, 1982.* The Eastern Cooperative Oncology Group, Robert Comis M.D., Group Chair.

### 11.2 Common Terminology Criteria for Adverse Events V4.03 (CTCAE)

The descriptions and grading scales found in the revised NCI Common Terminology Criteria for Adverse Events (CTCAE) version 4.03 will be utilized for adverse event reporting. (<http://ctep.cancer.gov/reporting/ctc.html>)

### 11.3 Immune Related Response Criteria (irRC) with Response Evaluation Criteria in Solid Tumors (RECIST) 1.1

Responses will be evaluated in all subjects. Because of direct clinical observations of immune cell influx into tumor causing enlargement in some patients prior to sustained response, recently it has been suggested that clinical trials involving the use of immunotherapy use alternative guidelines, called immune related response criteria (irRC) to determine radiographic response or progression after therapy. The criteria for evaluation of response are those defined in Wolchok JD, Hoos A, O'Day S, et al. Guidelines for the evaluation of immune therapy activity in solid tumors: Immune-related response criteria. Clin Cancer Res 2009; 15:7412-7420.

These recommendations have been used in recent clinical trials. One study of 227 subjects with metastatic melanoma showed that the approximately 10% of patients who had PD by modified WHO criteria but either CR, PR or SD by irRC had a similar overall survival as those patients who had SD, PR or CR by both criteria. The irRC was created using bidimensional measurements (as previously widely used in the WHO criteria). We have taken the concepts of the irRC and combined them with the recently revised RECIST 1.1 to come up with the modified irRC used in this protocol. Consistent with the irRC, the main changes from RECIST 1.1 are (a) a requirement for confirmation of both progression and response by imagining at least 4 weeks

after initial imaging and (b) not automatically calling the appearance of new lesions progressive disease if the total measurable tumor burden has not met criteria for progressive disease.

For immune-related response criteria (irRC), only index and measurable new lesions are taken into account. At baseline tumor assessment on this trial, target lesions will be measured along the longest axis and the measurements will be summed, called sum of largest diameter (SLD). These lesions must be a minimum of 10mm per lesion, maximum of 5 target lesions, maximum of 2 per organ system. At each subsequent tumor assessment, the unidimensional measurement of target lesions and of new measurable lesions are added together to provide the total tumor burden: As per the modified definitions below, all responses and progression except stable disease (SD) required confirmation on a consecutive scan at least 4 weeks from the initial observation).

Definitions of irRC:

Response	irRC
New measurable lesions	Incorporated into tumor burden
New non-measurable lesions	Do not define progression (but precludes irCR)
Non-index lesions	Contributes to defining irCR (complete disappearance required)
Overall irCR	100% disappearance of all lesions, whether measurable or not, and no new lesions, in two consecutive observations not less than 4 wks from the date first documented. All measurable lymph nodes also must have reduction in short axis to <10mm.
Overall irPR	≥ 30% decrease in SLD compared with baseline confirmed by a consecutive assessment at least 4 wk after first documentation
Overall irSD	Not meeting criteria for irCR or irPR, in absence of irPD: 30% decrease in SLD compared with baseline cannot be established nor 20% increase compared with nadir.
Overall irPD	At least 20% increase in SLD compared with nadir (minimum recorded tumor burden) and an increase of at least 5mm over the nadir, confirmed by a repeat, consecutive observation at least 4 wk from the date first documented.

Overall responses derived from changes in index, non-index and new lesions as demonstrated in the following table:

Measurable response	Non-measurable response		Overall response using irRC
Index and new, measurable lesions (tumor burden)* %	Non-index lesions	New, non-measurable lesions	
Decrease 100%	Absent	Absent	irCR&
Decrease 100%	Stable	Any	irPR&
Decrease 100%	Unequivocal progression	Any	irPR&
Decrease $\geq$ 30%	Absent / Stable	Any	irPR&
Decrease $\geq$ 30%	Unequivocal progression	Any	irPR&
Decrease < 30% to increase < 20%	Absent / Stable	Any	irSD
Decrease < 30% to increase < 20%	Unequivocal progression	Any	irSD
Decrease $\geq$ 20%	Any	Any	irPD

\* Decreases assessed relative to baseline

& Assuming response (irCR) and progression (irPD) are confirmed by a second, consecutive assessment at least 4 weeks apart.

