### **Measurable:**

A lesion, not previously irradiated per the protocol prior to enrollment, that can be accurately measured at baseline as  $\geq 10$  mm in the longest diameter (except lymph nodes which must have short axis  $\geq 15$  mm) with computed tomography (CT) or magnetic resonance imaging (MRI) and that is suitable for accurate repeated measurements. A tumor lesion in a previously irradiated field can be assessed as measurable disease provided the lesion has been deemed to demonstrate progression.

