### 4.2 Target lesions

#### 4.2.1 Documentation of target lesions

A maximum of 5 measurable lesions, with a maximum of 2 lesions per organ (including lymph nodes), representative of all lesions involved should be identified as TL at baseline. Target lesions should be selected on the basis of their size (longest diameter for non-nodal lesions or short axis for nodal lesions), but in addition should be those that lend themselves to reproducible repeated measurements. It may be the case that, on occasion, the largest lesion does not lend itself to reproducible measurement in which circumstance the next largest lesion, which can be measured reproducibly, should be selected.

The site and location of each TL should be documented as well as the longest diameter for non-nodal lesions (or short axis for lymph nodes). All measurements should be recorded in millimeters. At baseline the sum of the diameters for all TL will be calculated and reported as the baseline sum of diameters. At follow-up visits the sum of diameters for all TL will be calculated and reported as the follow-up sum of diameters.

Special cases:

- For TL measurable in 2 or 3 dimensions, always report the longest diameter. For pathological lymph nodes measurable in 2 or 3 dimensions, always report the short axis.
- If the CT/MRI slice thickness used is  $>5$  mm, the minimum size of measurable disease at baseline should be twice the slice thickness of the baseline scan.
- If a lesion has completely disappeared, the longest diameter should be recorded as 0 mm.

- If a TL splits into two or more parts, then record the sum of the diameters of those parts.
- If two or more TLs merge then the sum of the diameters of the combined lesion should be recorded for one of the lesions and 0 mm recorded for the other lesion(s).
- If a TL is believed to be present and is faintly seen but too small to measure, a default value of 5 mm should be assigned. If an accurate measure can be given, this should be recorded, even if it is below 5 mm.
- If a TL cannot be measured accurately due to it being too large, provide an estimate of the size of the lesion. Although a visit response of PD will be assigned in the vast majority of these cases, a case should be flagged and reviewed by the Study Physician in a blinded fashion if use of the estimated size in the calculation of TL would not give an overall visit response of PD.

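### Appendix 11.3 sums target lesions on the longest axis with no lymph-node exception, against the short-axis rule in 11.4, and its response table cannot return irCR for a target node that normalises but stays visible

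*Combined protocol and SAP*

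**What the plan says.** Appendix 11.3 sets out the trial's own immune-related criteria. It explains: "We have taken the concepts of the irRC and combined them with the recently revised RECIST 1.1". It names two main changes from RECIST 1.1: imaging confirmation of response and progression, and new lesions no longer counting automatically as progression.

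Its measurement rule is that "target lesions will be measured along the longest axis and the measurements will be summed, called sum of largest diameter (SLD". Its size rule is "These lesions must be a minimum of 10mm per lesion, maximum of 5 target lesions, maximum of 2 per organ system". Neither sentence mentions lymph nodes. Partial response (irPR) needs a "≥ 30% decrease in SLD compared with baseline". Complete response (irCR) needs "100% disappearance of all lesions, whether measurable or not, and no new lesions", and the same definition adds "All measurable lymph nodes also must have reduction in short axis to <10mm". In the response table that follows, irCR appears only where the summed burden of index and new measurable lesions falls by 100%.

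Appendix 11.4 has explicit nodal rules. Its definition of a measurable lesion is 10 mm or more in longest diameter, "except lymph nodes which must have short axis" of at least 15 mm. Nodes of 10 to under 15 mm short axis are non-measurable. Part 4.2.1 of the appendix says: "For pathological lymph nodes measurable in 2 or 3 dimensions, always report the short axis". Table 2 of the appendix accepts a target node below 10 mm short axis as part of a complete response, and Table 3 calls nodes below that size non-pathological.

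Sections 3.1.1, 8.2.1 and 8.3 make RECIST 1.1 response the primary Phase 2 endpoint. Sections 3.3 and 8.3 make irRECIST response exploratory.

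**The concern.** The trial will report two response rates from the same scans. The immune-related rate is informative only if it departs from the RECIST 1.1 rate for the reasons that 11.3 gives, namely confirmation and the handling of new lesions. If nodes are also summed on a different axis and admitted at a different size, the two rates can differ because of node shape, and a reader could take that for an immune-response pattern.

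Separately, 11.3 gives two answers for a target node that returns to normal size but can still be seen: its nodal sentence is met and its response table is not. Two people following the appendix could code the same patient as irCR and as irPR.

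**Working it through.** **Design figure, for context.** Section 8.4 gives 27 patients for 5% against 20%, 80% power and alpha 0.05. An exact single-stage binomial rule, taken as one-sided because sidedness is not stated, reproduces this. Success at 4 or more responses of 27 has alpha 0.0437 and power 0.818; with 26 patients the power is 0.793. The calculation concerns the primary response rate, which is RECIST 1.1, so nothing below enters it.

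**Inputs from the documents.**
- 11.3: longest axis for target lesions; minimum 10 mm; irPR at a 30% decrease or more; irCR row at a 100% decrease.
- 11.4: short axis for nodes; minimum 15 mm short axis; PR at a 30% decrease or more; target nodes below 10 mm short axis count towards CR.

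**Assumptions.** The documents give no lesion sizes. The sizes below (nodes as long x short axis, mm) are chosen for illustration. All nodes have a baseline short axis of at least 15 mm, so they are valid targets under both appendices. I assume no new lesions, no non-target progression, and the same measurements on the confirming scan.

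**Formula.** Change = (sum at follow-up / sum at baseline) - 1, with the node's longest axis under 11.3 and its short axis under 11.4.

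| Case | 11.3, longest axis | 11.4, node short axis |
|---|---|---|
| A. Liver 40 to 30; node 22x16 to 18x9 | (30+18)/(40+22) - 1 = 48/62 - 1 = -22.6%, irSD | (30+9)/(40+16) - 1 = 39/56 - 1 = -30.4%, PR |
| B. Node 24x18 to 18x12 | 18/24 - 1 = -25.0%, irSD | 12/18 - 1 = -33.3%, PR |
| C. Node 30x16 to 20x13 | 20/30 - 1 = -33.3%, irPR | 13/16 - 1 = -18.8%, SD |
| D. Liver 30 to 0; node 24x16 to 12x7 | (0+12)/(30+24) - 1 = 12/54 - 1 = -77.8%, irPR row | all target-lesion conditions for CR met |
| E. Node 24x16 to 0 | -100%, irCR row | -100%, CR |

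Cases A and B lose a response under 11.3, and case C gains one. The direction depends on which axis shrinks more.

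Case D is the internal conflict. The node's short axis is 7 mm, so the nodal sentence in the irCR definition is met. Its longest axis is still 12 mm, so the burden has not fallen by 100% and the table gives irPR. Case E shows the limit of the problem: a node that vanishes reaches irCR under the table as written.

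**Size rule.** Nodes of 18x12 and 20x14 mm pass the 11.3 minimum but are non-measurable under 11.4. Nodes of 10x6, 12x8 and 14x9 mm also pass the 11.3 minimum, although 11.4 calls them non-pathological.

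**The case against.** The best defence is that 11.3 never says nodes are measured on the longest axis; it only omits an exception. It is built on RECIST 1.1 and does not announce a change of nodal rule, so the RECIST nodal rules may have been meant to carry over. The short-axis sentence in the irCR definition fits that: it has little purpose unless residual nodes below 10 mm are compatible with irCR. Section 5.2 (inclusion criterion 3) also refers to 11.4 for the definition of target lesions. This is probably what was intended, and it supports the fix. It does not remove the defect. The reference in 5.2 sits in a Phase 2 eligibility criterion, and the measurement sentence in 11.3 is specific to this trial and has no exception. Even with identical target lesions, the axis still conflicts.

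Four stronger readings are tempting, and the documents do not support them.
- *irCR is impossible with any nodal target.* Case E shows otherwise. The problem is confined to nodes that normalise without vanishing.
- *Normal nodes will be used as targets and dilute real shrinkage.* On assumed sizes, a liver lesion going from 40 to 27 mm is -32.5% alone and (27+12)/(40+12) - 1 = -25.0% with one unchanged 12 mm node in the sum. But this needs a reader to select as a tumour target a node that 11.4 calls non-pathological. The 11.3 size rule permits that on its own; nothing directs it.
- *The irRECIST rate is biased downward.* Case C goes the other way.
- *Any difference between the two sums is an error.* 11.3 deliberately adds new measurable lesions to the burden, so some difference is by design.

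**Conclusion.** The rule in 11.3 is wrong as written, in two respects. It conflicts with 11.4 on nodal axis and minimum size without listing this as a change from RECIST 1.1. It also conflicts with itself for a target node that falls below 10 mm short axis but remains visible, for which its table cannot return irCR.

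For an individual patient the effect can be a change of category: PR to irSD in cases A and B, SD to irPR in case C, and a target-lesion CR to irPR in case D. All lesion sizes are assumptions. The number of patients affected depends on how many have nodal targets and how those nodes change shape, neither of which the documents give, so no shift in the irRECIST rate can be estimated.

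The consequence is limited to an exploratory endpoint. The primary RECIST 1.1 analysis and the sample size of 27 stand. Section 4.2.3 does call the immune RECIST response rate primary, and a reader might infer that the primary result is at risk. Sections 3.1.1, 8.2.1 and 8.3 all say otherwise, so that sentence is a separate inconsistency. The defect would reach the primary analysis only if 4.2.3 were followed.

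**What to change.** Add two sentences to 11.3.

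1. The immune-related criteria use the same baseline target lesions and the same measurements as 11.4: non-nodal lesions by longest diameter, at least 10 mm; lymph nodes by short axis, at least 15 mm at baseline.
2. In the response table, a target node with a short axis below 10 mm counts as satisfying the 100%-decrease row for irCR.

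The wording of the irCR definition should be brought into line with the second sentence. The rules on confirmation and on adding new measurable lesions stay as they are.

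The cost is a short text change. It needs no extra scans and no second set of node measurements for target lesions, because 11.4 already requires the short axis. Differences between the two response rates would then no longer arise from how target nodes are selected and measured.

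### Section 11.3 words irPR, irSD and irPD on SLD (target lesions only), while its text, new-lesion row, nadir gloss and matrix heading use total tumor burden, so one patient can get two immune-response categories

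*Combined protocol and SAP*

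**What the plan says.** Section 11.3 of the combined protocol and SAP introduces two quantities. For baseline it states that "target lesions will be measured along the longest axis and the measurements will be summed, called sum of largest diameter (SLD" is the abbreviation used. For every later assessment it states that "the unidimensional measurement of target lesions and of new measurable lesions are added together to provide the total tumor burden". It also says that "only index and measurable new lesions are taken into account", and it gives as one of two main departures from RECIST 1.1 "not automatically calling the appearance of new lesions progressive disease if the total measurable tumor burden has not met criteria for progressive disease".

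The table of irRC definitions then uses both terms:

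- New measurable lesions: "Incorporated into tumor burden".
- irPR: "≥ 30% decrease in SLD compared with baseline confirmed by a consecutive assessment at least 4 wk after first documentation".
- irSD: "30% decrease in SLD compared with baseline cannot be established nor 20% increase compared with nadir".
- irPD: a rise in SLD of at least 20% and at least 5 mm over the nadir, where the nadir is explained in parentheses as the lowest tumor burden recorded.

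The overall-response matrix that follows is scored on a column headed "Index and new, measurable lesions (tumor burden" and closed with a percentage sign. Its irPD row is printed as a decrease, not an increase, of 20% or more.

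On the role of the endpoint, sections 3.1.1, 8.2.1 and 8.3 make response by RECIST 1.1 the Phase II primary endpoint, and sections 3.3 and 8.3 make irRECIST response exploratory. Section 4.2.3 instead calls the immune RECIST response rate primary.

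**The concern.** A response rule should return one category per patient. Here the rows that define irPR, irSD and irPD name a quantity that the text restricts to target lesions. The text and the matrix use a quantity that also contains new measurable lesions. The two are equal at baseline, when no lesion is new, and separate as soon as a new measurable lesion appears. That is the situation the immune criteria were adopted to handle.

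The irRECIST response rate is a planned endpoint. An assessor who applies the defined term SLD as written would count as responders some patients whose total burden has not fallen by 30%. The resulting error in the rate is one-directional: adding new lesions can only make burden larger than the target sum, so a literal SLD reading can add responders relative to the burden reading and cannot remove any.

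**Working it through.** The plan states no figure on this point to reproduce, so the check applies the thresholds of section 11.3 to example patients, scored once on each quantity.

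**Inputs.** B = baseline SLD; T = target-lesion sum at the visit; N = sum of new measurable lesions. irPR needs a fall of at least 30% from baseline. irPD needs a rise of at least 20% and at least 5 mm over nadir. The lesion sizes are illustrative. Each example is a first on-study scan, so nadir = baseline, and the finding is taken as confirmed at the next scan.

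**Formulas.** SLD change = (T - B)/B. Burden change = (T + N - B)/B.

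| B (mm) | T (mm) | N (mm) | SLD change | Category on SLD | Burden change | Category on burden |
|---|---|---|---|---|---|---|
| 100 | 65 | 10 | -35% | irPR | (75 - 100)/100 = -25% | irSD |
| 100 | 65 | 20 | -35% | irPR | (85 - 100)/100 = -15% | irSD |
| 100 | 65 | 60 | -35% | irPR | (125 - 100)/100 = +25% | irPD |
| 100 | 100 | 25 | 0% | irSD | (125 - 100)/100 = +25%, +25 mm | irPD |
| 50 | 50 | 10 | 0% | irSD | (60 - 50)/50 = +20%, +10 mm | irPD |

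**When irPR is lost.** A patient is irPR on SLD but not on burden when T ≤ 0.7B and T + N > 0.7B, that is, when N > 0.7B - T. With B = 100 and T = 65 this is N > 5 mm. Section 11.4 sets the smallest measurable lesion at 10 mm, so any single new measurable lesion changes this patient's category.

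**Does the matrix arbitrate?** Reading its percentage rows as printed:

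- -15% matches irSD only, so the second example is a clean conflict between the irPR definition and the matrix.
- -25% matches both irSD and irPD; -35% matches both irPR and irPD.
- +25% matches no row.

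For irPD, then, the conflict is between the definition and the text of section 11.3. The matrix as printed gives no category to a rise of 20% or more.

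**Effect on the rate.** With 27 Phase II patients, one reclassified patient moves the irRECIST rate by 1/27 = 3.7 percentage points.

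**Effect on the sample size.** None. Section 8.4 plans 27 patients for 5% versus 20%. Rejecting at 4 or more responses gives exact one-sided alpha 0.0437 and power 0.818, so the figure reproduces, and it concerns the RECIST 1.1 endpoint.

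**The case against.** The best answer is that the intended meaning is visible. The definitions table itself places new measurable lesions in tumor burden, the irPD row explains its nadir as a burden, and the text and matrix heading agree. SLD is named in a sentence about baseline, when the two quantities coincide, so its later use can be read as loose shorthand for the running sum. This stands as far as intent goes. It does not remove the defect: SLD has a stated meaning, three rows use it, and the irPD row taken literally compares a target-only sum with a nadir that may include new lesions.

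Three stronger readings are tempting, and the documents do not support them.

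- *New measurable lesions are ignored, and on their own can never produce irPD.* This requires reading three cells apart from the first row of their own table and from the irPD row's parenthesis.
- *The matrix assigns irPD on burden where the definitions assign irSD.* It does not, because its irPD row is printed as a decrease.
- *Most immune responders would be misclassified.* Such figures depend on assumed lesion sizes and apply only to patients who have a new lesion. If baseline SLD is uniform on 40 to 120 mm, target shrinkage uniform on 30 to 60%, and there is one new lesion of 10 to 20 mm, 66% of SLD responders with a new lesion are not irPR on burden. Changing only the baseline range to 80 to 200 mm lowers this to 38%. The documents support neither set of inputs.

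It is also fair to say that the stakes are limited. Sections 3.3 and 8.3 make irRECIST exploratory, and under the RECIST 1.1 appendix a new lesion is progression whatever the targets do.

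**Conclusion.** The concern holds as an inconsistency of terms with a real consequence if followed literally. The same patient can be irPR or irSD, or irSD or irPD, depending on which defined quantity is used, and the printed matrix does not resolve irPD.

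The direction of the effect is known only conditionally: a literal SLD reading would raise the irRECIST response rate. Nothing shows that assessors would read it that way, so a reader should not infer that the reported rate will be biased. The size is unknown, because the documents do not say how often a new measurable lesion accompanies target shrinkage of 30% or more; the unit is 3.7 points per patient among 27.

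The primary analysis by RECIST 1.1 and the sample size are untouched. This rests on sections 3.1.1, 8.2.1 and 8.3 governing. If section 4.2.3 governed, the same ambiguity would sit in the primary endpoint, so that conflict should be settled as well.

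**What to change.** 1. In the irPR, irSD and irPD rows of section 11.3, replace SLD with total tumor burden (target plus new measurable lesions). Name baseline SLD as the reference for decreases and nadir total tumor burden as the reference for increases.
2. Reconcile the matrix irPD row with the irPD definition, so that it describes an increase of at least 20% over nadir. Without this step, rewording the three rows would still leave the matrix without a category for progression.
3. Bring section 4.2.3 into line with sections 3.1.1, 8.2.1 and 8.3 on which response criterion is primary.

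The cost is a few cells and one sentence, with no added scans, visits or patients. The exploratory irRECIST rate may come out slightly lower than under a literal SLD reading. The wording should be settled before responses are scored.
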